## 4 ANALYSIS POPULATIONS (ANALYSIS SETS)

The populations defined in this section guide the selection of subjects for a given set of listings.

### 4.1 Efficacy Population

All subjects who enroll in the study and receive at least one dose of study treatment and have a post-baseline visit will be included in the efficacy population.

### 4.2 Safety Population

All subjects who enroll in the study and receive at least one dose of study treatment will be included in the Safety Population. This will be the population for the safety analyses, as well as for presentation and summarization of baseline/demographic characteristics and subject disposition.

### 4.3 Pharmacokinetic Population

The PK Population will include all subjects who undergo PK sampling and have evaluable concentration-time data for analysis.

### 4.4 Pharmacodynamic Population

The PD population will include all subjects who have a baseline measure, along with a post baseline measure and receive at least one dose of study treatment.

## 5 TREATMENT DESCRIPTIONS

Unless otherwise indicated, the treatment will be identified by RVT-1401 680 mg/week (Cohort 1).

## 6 STATISTICAL ANALYSIS METHODS AND ISSUES

### 6.1 Statistical Methods

All available data will be presented in the data listings.

### 6.2 Missing Data

Other than missing dates as described below, no imputation methods will be used for missing data.

#### **Missing dates are imputed in the following cases:**

For the analysis of safety variables, only partial dates may be imputed; otherwise, missing data will be treated simply as missing. The algorithms for imputation of partial dates depend upon the parameter.

*Adverse Event Onset*

Dated 10 December 2021

- If onset date is completely missing, date is set to date of first dose. If onset time is missing, the time will not be imputed.
- If year is present and month and day are missing or year and day are present and month is missing:
  - If year = year of first dose, then set month and day to month and day of first dose.
  - If year < year of first dose, then set month and day to December 31.
  - If year > year of first dose, then set month and day to January 1.
- If month and year are present and day is missing:
  - If year = year of first dose and
    - month = month of first dose, then set day to day of first dose date.
    - month < month of first dose, then set day to last day of month.
- For all other cases, set date to date of first dose.

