#### *Adverse Event End Date*

- If year is present and month and day are missing or year and day are present and month is missing, set end month and day to December 31.
- If month and year are present and day is missing, set the day to last day of the month.
  - If fatal event, date is set to minimum of imputed end date and death date.
  - For all other cases, set date to missing.

The imputed dates must be logical, ensuring that no end date is after database lock or death or before the start date.

If site queries fail to resolve partial dates for laboratory values and vital signs, the date is missing and will not be imputed.

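### Adverse event onsets with only the day missing are moved to the first-dose date whenever the recorded month is later or in another year (minor)

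*SAP*

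**What the plan says.** SAP 6.2 keeps date imputation active although Version 3.0 is a listings-only plan: "Other than missing dates as described below, no imputation methods will be used for missing data". For adverse event onset the rules are:

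- Date wholly missing: first-dose date. On time of day, "If onset time is missing, the time will not be imputed".
- Month missing (with or without the day): first-dose month and day if the year is that of first dose. Otherwise "If year < year of first dose, then set month and day to December 31" and "If year > year of first dose, then set month and day to January 1".
- Only the day missing: two sub-rules, both conditional on the year being that of first dose. For the same month, the day becomes the first-dose day. For an earlier month, "month < month of first dose, then set day to last day of month".
- Anything not covered: "For all other cases, set date to date of first dose".

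SAP 9.1 defines a treatment-emergent adverse event (TEAE) as one with onset after first treatment. It plans a TEAE listing, a serious TEAE listing and a by-subject adverse event listing with start and end dates. SAP 6.3 makes the first-dose date Day 1.

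**The concern.** The day-missing branch has no sub-rule for a later month in the first-dose year, or for any month in an earlier or later year. Those cases drop to the fallback and take a date that the recorded month rules out. It makes no difference whether the fallback bullet is read as belonging to that branch or to the whole list.

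The SAP is also inconsistent with itself. Knowing only that the year differs gives a date on the correct side of first dose. Knowing the month as well moves the same event to the first-dose date, so more information gives a worse date.

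Two things are at stake. Events known to be post-dose acquire a Day 1 onset with no time, and the SAP does not say whether that counts as after first treatment. Less often, an event known to be pre-dose because it belongs to the previous year is moved forward to Day 1 and could enter the TEAE listings.

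**Working it through.** The plan states no figure for this rule, so the check applies the rule literally.

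**Worked examples.** The first-dose dates are hypothetical; the documents give none.

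| First dose | Recorded onset | Date under SAP 6.2 | Date if only the year were known | Date under the fix |
|---|---|---|---|---|
| 15 Jun 2020 | Sep 2020 | 15 Jun 2020 | 15 Jun 2020 | 1 Sep 2020 |
| 10 Nov 2020 | Jan 2021 | 10 Nov 2020 | 1 Jan 2021 | 1 Jan 2021 |
| 10 Nov 2020 | Mar 2021 | 10 Nov 2020 | 1 Jan 2021 | 1 Mar 2021 |
| 10 Jan 2021 | Dec 2020 | 10 Jan 2021 | 31 Dec 2020 | 31 Dec 2020 |

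The last row is a pre-dose event moved onto Day 1.

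**Reach of the rule.** The inputs are three follow-up lengths F:

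- 21 days (3 × 7): SAP 1 reports one subject terminated after Week 3.
- 84 days (12 × 7): the 12-week treatment period.
- 134 days (19 × 7 + 1): the nominal day of the Week 20 visit.

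Assumptions: first-dose dates uniform over the 365 days of a year, and onsets uniform over days 1 to F. Every first-dose date is crossed with every onset day, giving 365 × F combinations. The share outside the recorded month is the number of combinations whose imputed month differs from the true month, divided by 365 × F.

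| | F = 21 | F = 84 | F = 134 |
|---|---|---|---|
| Combinations | 7,665 | 30,660 | 48,910 |
| Outside recorded month, current rule | 2,520 (32.9%) | 24,922 (81.3%) | 43,172 (88.3%) |
| Mean backward shift of those (days) | 13.7 | 48.8 | 74.0 |
| Placed on Day 1, current rule | 100% | 100% | 100% |
| Placed on Day 1, fixed rule | 67.1% | 18.7% | 11.7% |
| Outside recorded month, fixed rule | 0% | 0% | 0% |
| Mean error of the affected onsets, fixed rule (days) | 6.3 | 13.6 | 14.1 |

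The onsets left on Day 1 by the fix are the same-month cases, where the first-dose date is a reasonable choice.

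**Onsets in a later calendar year.** Here the day-missing rule can be compared with the SAP's own year-only rule.

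| | F = 21 | F = 84 | F = 134 |
|---|---|---|---|
| Share of post-dose onsets | 2.7% | 11.4% | 18.2% |
| Mean error, current day-missing rule (days) | 13.7 | 55.7 | 89.0 |
| Mean error, SAP year-only rule (days) | 6.3 | 27.3 | 44.0 |

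The mean error with the month known is about twice that with the month unknown.

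**Prior-year route.** Over the 30 days before first dose there are 365 × 30 = 10,950 combinations. The onset falls in the previous year in 465 of them (4.2%), all with first dose on 1 to 30 January. The mean error there is 20.3 days, against 9.7 days under the year-only rule.

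**Effect on TEAE status.** No single Day 1 convention repairs the current rule. Counting onsets on or after the first-dose date admits the pre-dose event in the last example row. Counting only onsets strictly after that date drops the certain post-dose events in the other three rows.

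**The case against.** The text and the arithmetic are not in dispute; the case on the other side is about consequence.

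- **The TEAE ambiguity comes from SAP 9.1, not from this rule.** It also affects wholly missing, year-only and same-month dates, all of which rightly stay at the first-dose date. One sentence in SAP 9.1 would settle it for post-dose onsets. This stands in part: the sentence is needed in any case, but the fallback is what carries clearly post-dose events onto Day 1, and the sentence would not correct their dates or the prior-year route.
- **The pattern suggests that a first-dose-date onset is meant to count as a TEAE.** That is plausible. Post-dose events would then be classified correctly and only their dates would be wrong. The SAP does not say so.
- **The wrong date may never be printed.** SAP 6.1 says "All available data will be presented in the data listings", and SAP 1 says derived variables were removed, both of which favour printing recorded dates. SAP 9.1 does not say which start date is listed. If it is the recorded one, only classification is affected.
- **Events dropped from the TEAE listing should still appear in the by-subject listing.** SAP 9.1 does not word that listing as limited to TEAEs. This stands and limits the harm.
- **The prior-year route is narrow.** Protocol 11.3 lets some post-consent events go to medical history instead. A recorded pre-dose end date would also trip the check "The imputed dates must be logical, ensuring that no end date is after database lock or death or before the start date".
- **There may be no such onsets.** Adverse events are reviewed at every visit, weekly through Week 14. This stands; the percentages show how far the rule reaches, not how many events to expect.

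**Conclusion.** The rule is wrong as written. For an onset with only the day missing, a later month or any month in another year is replaced by the first-dose date, contradicting the recorded month. For another year it is also less accurate than the SAP's own year-only rule. If such onsets occur, about a third (21 days of follow-up) to nearly nine in ten (134 days) of the post-dose ones would leave their recorded month, under the uniform-date assumptions.

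The consequence is minor. It is confined to adverse event listings for 5 Cohort 1 subjects, and no rates, durations or time-to-onset analyses are planned. The number of affected events is unknown. The safety listings still deserve to be right: the study was paused over a suspected drug effect on lipids, and with no summaries planned the listings are the only safety output under this SAP.

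**What to change.** In SAP 6.2, replace the day-missing rules for onset with a comparison of year and month together:

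- Same month and year as first dose: the first-dose date.
- Earlier month and year: the last day of the recorded month.
- Later month and year: the first day of the recorded month.

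Keep the first-dose default for wholly missing dates, and leave the year-only rules unchanged.

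In SAP 9.1, add two statements. First, an onset on the first-dose date with no recorded time counts as a TEAE; this is needed even after the change, because same-month cases stay on Day 1. Second, listings print the recorded partial date, and any imputed date serves only to classify TEAEs.

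The cost is a few lines of SAP text and one programming change. Data collection is not affected.

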#### *Adverse Event End Date*

- If year is present and month and day are missing or year and day are present and month is missing, set end month and day to December 31.
- If month and year are present and day is missing, set the day to last day of the month.
  - If fatal event, date is set to minimum of imputed end date and death date.
  - For all other cases, set date to missing.

The imputed dates must be logical, ensuring that no end date is after database lock or death or before the start date.

If site queries fail to resolve partial dates for laboratory values and vital signs, the date is missing and will not be imputed.

### **6.3 Data Issues**

Unless otherwise noted, values reported as greater than or less than some quantifiable limit (e.g., <1.0) will include the sign in all listings.

If there are multiple assessments collected on the same scheduled time, all values will be displayed. All data from all visits will be eligible for inclusion in the listings.

Study day is the day relative to the date of first dose. Day 1 is defined as the date of first dose, unless otherwise specified for the calculation of baseline.

For visits (or events) after first dose, day is calculated as:

- Study day = visit (or event) date - date of first dose + 1

For visits (or events) before first dose, day is calculated as:

- Study day = visit (or event) date - date of first dose

Dated 10 December 2021

## **6.4 Baseline Definition**

Baseline is the last available assessment prior to time of the first dose unless it is specified otherwise.

Subject's age in years at baseline is defined as the age derived at Screening in the EDC system.

## **7 DISPOSITION, DEMOGRAPHICS AND BASELINE CHARACTERISTICS**

### **7.1 Subject Disposition and Exposure**

The disposition listing will include the disposition of treatment and discontinuation of study by each subject. For discontinuations, the listing will include the reason for discontinuation.

Disposition of subjects in the Follow-up Period will be presented in listings.

Administration of RVT-1401 will be presented in listings denoting each visit and dose, and the treatment satisfaction questionnaire will be listed by treatment and by visit.

WAIHA treatment listing will also be provided.

### **7.2 Demographics and Baseline Characteristics**

The demographics (age, gender, race, ethnicity, and childbearing potential if female) and baseline characteristics (height, weight, body mass index) will be presented in listings.

[figure not shown]
### **7.3 Prior WAIHA treatment**

Based on the coded data of prior WAIHA medication(s) using the World Health Organization (WHO) Drug Reference List, the data will be presented in listings per the Anatomical Therapeutic Chemical (ATC) classification.

## **8 ANALYSIS OF EFFICACY ENDPOINTS**

Each endpoint noted below will be presented in a listing.

- FACIT-F score
- MRC breathlessness scale
- EQ-5D-3L score

Dated 10 December 2021

## 9 ANALYSIS OF SAFETY ENDPOINTS

Safety analyses will be performed on the Safety population unless otherwise indicated.

### 9.1 Adverse Events

The adverse events (AEs) will be coded by the Medical Dictionary for Drug Regulatory Activities (MedDRA) version 22.1 or higher. A treatment-emergent adverse event (TEAE) is defined as any AE onset post first treatment. A listing of all subjects reporting TEAEs will be presented. A separate listing of serious TEAEs will be provided. A by-subject listing containing the AEs by the MedDRA system organ class and preferred term will be created. This listing will include start and end dates of the event, severity, and relationship to study drug. Injection site reactions will also be presented in a separate listing.

The AE data will not be imputed other than a missing date.

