6.9. Toxicity Management Criteria

6.9.1. Toxicity Management Criteria (AEs, Cardiovascular, and Injection Site Reactions)

The severity of each AE will be graded and managed according to the criteria in Table 2 (CTCAE version 5.0). Study drug should be permanently discontinued for any grade 4 toxicity other than hemoglobin decrease. Management of hemoglobin < 7.0 g/dL or anemia in the presence of cardiovascular symptoms is described in section 6.9.2. For grade 3 TEAE not considered related to WAIHA signs/symptoms, study drug should be withheld. Study drug may only be restarted following a grade 3 TEAE after discussion with the medical monitor. Table 2 Criteria for Determining the Grade/Severity of Adverse Event Terms

Grade	Criteria
1/Mild	Asymptomatic or mild symptoms, clinical or diagnostic observations only; intervention not indicated
2/Moderate	Limiting age-appropriate instrumental activities of daily living; minimal, local, or noninvasive intervention as indicated
3/Severe or medically significant	Not immediately life-threatening; hospitalization or prolongation of hospitalization indicated; disabling; limiting self-care activities of daily living, intervention as indicated
4/Life-threatening	Life threatening consequences; urgent intervention indicated
5/Death	Death related to adverse event

Injection Site Reactions

Injection site evaluations will be made by clinical staff following administration of RVT-1401 as described below. Additional details related to the specific injection site location will be included within a study specific manual. If an injection site reaction is observed, a physician will characterize and document the reaction as an AE. Review of the injection site will continue until the AE is resolved. Symptomatic treatment (e.g., warm compresses, topical steroids, antihistamines if itching is present, or NSAIDs) may be provided for injection site reactions at the discretion of the Investigator.

The injection sites will be monitored for pain, tenderness, erythema and swelling. Each injection site reaction will be categorized using the intensity grading scheme presented in Table 3.

Table 3 Criteria for Determining the Grade/Severity of Injection Site Reactions

Grade	Criteria
1/Mild	Tenderness with or without associated symptoms (e.g., warmth, erythema, itching)
2/Moderate	Pain; lipodystrophy; edema; phlebitis
3/Severe or medically significant	Ulceration or necrosis; severe tissue damage; operative intervention indicated

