11.1. Definition of Adverse Events

An AE is any untoward medical occurrence in a participant or clinical investigation participant, temporally associated with the use of a medicinal product, whether or not considered related to the medicinal product.

An AE can therefore be any unfavorable and unintended sign (including an abnormal laboratory finding), symptom, or disease (new or exacerbated) temporally associated with the use of a medicinal product.

Events meeting the definition of an AE **include but are not limited to:**

- Any clinically significant, new or worsened, abnormal laboratory test results (hematology, clinical chemistry, or urinalysis) or other safety assessments (e.g., ECGs, radiological scans, vital signs measurements). Clinical significance is determined based on the medical and scientific judgement of the Investigator.
- Signs, symptoms, or the clinical sequelae of a suspected interaction (e.g. with medications or food).
- Signs, symptoms, or the clinical sequelae of an overdose of either investigational product or a concomitant medication (overdose without an AE should be reported as a protocol deviation).

Events that **do not** meet the definition of an AE include:

- Anticipated day-to-day fluctuations of pre-existing condition(s), including the disease under study.
- Abnormal or worsening laboratory, imaging, or other safety findings that are not clinically significant.
- Medical or surgical procedures (e.g., endoscopy, appendectomy); the condition that leads to the procedure is an AE.
- Situations where an untoward medical occurrence did not occur (social and/or convenience admission to a hospital).

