11.3. Time Period and Frequency for Collecting AE and SAE Information

- AEs will be collected from the time of informed consent through the follow-up period, at the timepoints specified in the Section 8.1, Time and Events Table.
- Medical occurrences that begin prior to any study procedure but after obtaining informed consent may be recorded on the Medical History/Current Medical Conditions section of the eCRF.
- All SAEs will be recorded and reported to the Sponsor within 24 hours of site awareness.
- Any SAEs assessed as related to study participation (e.g., protocol-mandated procedures, invasive tests, or change in existing therapy) or related to investigational product will be recorded from the time a participant consents to participate in the study up to and including any follow-up contact.

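### SAP 9.1 defines treatment-emergence by onset alone, so a pre-dose AE that worsens or turns serious on drug can be absent from the TEAE and serious-TEAE listings

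*SAP*

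**What the plan says.** SAP 9.1 gives the definition: "A treatment-emergent adverse event (TEAE) is defined as any AE onset post first treatment". It contains no clause for an event already present at first dose that later changes.

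Two outputs depend on it: "A listing of all subjects reporting TEAEs will be presented", and "A separate listing of serious TEAEs will be provided". A third does not: "A by-subject listing containing the AEs by the MedDRA system organ class and preferred term will be created". Of that third listing SAP 9.1 adds: "This listing will include start and end dates of the event, severity, and relationship to study drug".

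Protocol 11.3 sets the collection window: "AEs will be collected from the time of informed consent through the follow-up period". Protocol 5.1 allows a screening period of up to 4 weeks. Protocol 11.1 includes in its AE definition any "disease (new or exacerbated) temporally associated with the use of a medicinal product", and it also names clinically significant laboratory results that have worsened.

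The protocol uses the term TEAE in its toxicity rules (6.9.1): "For grade 3 TEAE not considered related to WAIHA signs/symptoms, study drug should be withheld". It does not define the term there or elsewhere.

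**The concern.** A treatment-emergent definition should pick out what happened on drug. Worsening on drug of something that began a week or two earlier belongs in that group, particularly if it becomes serious. A rule based only on the start date leaves it out.

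Safety and tolerability form one of the two primary endpoints, and the SAP introduction records that the study was paused over a suspected drug effect on lipids. SAP Version 3.0 is confined to listings, so no summary table would bring such an event to notice. What a reader sees as the on-treatment safety experience depends on which events the listings admit, and treatment-emergent status still decides membership of two of them.

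**Working it through.** No arithmetic applies. The documents state no figure that depends on the definition, so the check is to set the relevant sections side by side.

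1. **Can an AE be on record before first dose?** Yes. Collection starts at consent (Protocol 11.3) and screening can last up to 4 weeks (Protocol 5.1). One route is closed: an occurrence after consent but before any study procedure may go to medical history instead.
2. **Can a subject be dosed with such an AE ongoing?** Yes, within limits. Exclusion 10 removes a subject with a screening laboratory abnormality only if the investigator judges it clinically significant, unresolved at baseline, and a threat to participation. Exclusion 12 bars active infection, so an infection carried into dosing is a poor example. Laboratory or disease-related events fit better.
3. **Does worsening open a new record?** Neither document says so. Protocol 11.7 has each event followed until it resolves or stabilises, and Protocol 11.2 has seriousness marked on the AE form. Both are compatible with one record that keeps its screening onset date. Protocol 11.1 equally allows a site to enter the worsening as an AE in its own right.
4. **Does another SAP rule rescue the event?** No. The date imputation in SAP 6.2 acts on missing or partial onset dates, so it does not touch a known screening date.

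Applying the rule to illustrative cases (the days are chosen only to show the logic):

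| Case | TEAE listing | Serious-TEAE listing | By-subject AE listing |
|---|---|---|---|
| Onset day -5 at grade 1, grade 3 on day 20, one record | Absent | Not applicable | Present |
| Onset day -5, becomes serious on day 20, one record | Absent | Absent | Present, but seriousness is not a named content |
| Same course, worsening entered as a new AE on day 20 | Present | Present if serious | Present |
| Condition held in medical history, worsening entered as an AE on day 20 | Present | Present if serious | Present |

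The same clinical course is treatment-emergent or not according to how the site entered it. In the single-record cases the stated rule gives the wrong classification.

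**The case against.** The strongest reply is that nothing disappears. The by-subject listing covers AEs generally and carries dates, severity and relationship. SAP 6.1 puts all available data in the listings, and Protocol 10.3.4 plans to list every AE, serious or not. Laboratory results, vital signs and ECGs have listings of their own. With 5 subjects, a reader can go through the full AE listing line by line. This stands. A reader might infer that these events are lost from the report, or that the two TEAE listings are the whole safety result, and the documents support neither inference. What remains is that SAP 9.1 does not name seriousness as a content of the by-subject listing, and the one listing devoted to serious events admits only TEAEs.

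The second reply is that worsening may be entered as a new AE, which Protocol 11.1 allows. This also stands as a possibility, so it would be too strong to say that every such event is misclassified. But neither document requires it, and a definition should not depend on site habit.

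A reader might also infer from Protocol 6.9.1 that the SAP definition governed when drug was withheld. The documents do not support that: withholding is a decision made under the protocol during dosing, and this SAP version was written after the pause, for reporting Cohort 1. What stands is only that the protocol uses a term it does not define.

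**Conclusion.** The point holds in limited form. SAP 9.1 states a rule that leaves a pre-dose AE which worsens or becomes serious on drug out of the TEAE listing and the only dedicated serious-event listing, when the event is kept as one record. The event still appears in the by-subject AE listing, where its seriousness may not be visible.

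The size is small. At most 5 subjects are involved and no rate, test or interval uses TEAE status. The documents give no count of AEs ongoing at first dose and no frequency of worsening, so the number affected cannot be derived and may be zero. Expressing a missed event as a percentage of the cohort would describe a statistic that this SAP does not produce.

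The conclusion assumes that at least some sites keep worsening within the existing record. The public documents neither confirm nor exclude this. The change is worth making because the rule is explicit, the gap concerns serious events, and the correction costs almost nothing.

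**What to change.** - **Definition (SAP 9.1).** Define a TEAE as an AE that starts on or after first dose, or that was present before first dose and increases in severity or becomes serious afterwards. Saying on or after also settles events whose missing onset date SAP 6.2 sets to the day of first dose without imputing a time.
- **By-subject AE listing (SAP 9.1).** Add a seriousness column, so that a serious event can be recognised whatever its onset date.
- **Applying it.** The documents do not say whether the AE form keeps successive grades or the date an event became serious. If it does not, the records of 5 subjects can be checked by hand.
- **Term in the protocol.** Protocol 6.9.1 uses TEAE undefined. The sponsor should reconcile the term across the two documents. No clinical rule is proposed here.

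The cost is one sentence in the SAP, one added column, and a re-run of the AE listings. No new data collection is needed unless the hand check raises a query.
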